# 9.2. Sample Size

For Part A, the goal of the study is to study infant PK, and therefore no formal sample size calculation will be conducted.

For Part B, the sample size estimation is based on the primary efficacy endpoint of medically attended RSV infection (hospitalization or outpatient LRTI). Literature (Hall 2009, Ambrose 2014) show that the event rate in this endpoint is in the range of 12% to 22% in the studied infant populations. As the event rate may vary over RSV season or geographic region, it is assumed that event rate is 10% for the placebo group, and either dose of RENG2222 would reduce the event rate from placebo by 60% (event rate of 4%). With 505 randomized subjects per arm or a total of 1515 randomized subjects, the study has 90% power to demonstrate a 60% or greater reduction at 2-sided significance level  $\alpha$ =0.025. This sample size also incorporated a 5% early dropout rate. The sample size calculation is based chi-square test with continuity correction and performed using nQuery version 7.0 (Statistical Solutions Ltd, Cork, Ireland).

The significant level of 2-sided 0.025 is set in consideration of multiplicity of 2 comparisons between each of the 2 REGN2222 dose arms with placebo.

With a total of 1515 randomized subjects and 1:1:1 randomization ratio, it is expected 1010 subjects to receive REGN2222 (505 subjects in each of the 2 REGN2222 arms) and 505 subjects to receive placebo and in total, an approximate of 90 primary endpoint events. Also, with 1010 subjects exposed to REGN2222, the regulatory requirement for safety assessment will be met.

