# 9.5.2.1. Primary Efficacy Analysis

#### Part B

The primary endpoint will be analyzed using Mantel-Haenszel methods to assess the differences in the proportions between each REGN2222 treatment and placebo, stratifying by region (North America or rest of the world) and GA (≤31 weeks, 6 days GA or from 32 weeks, 0 days to 35 weeks, 6 days GA).

The proportion of primary endpoint events for primary analysis will be calculated as number of subjects with a medically attended RSV infection (hospitalization or outpatient RSV LRTI) during the 150-day efficacy assessment period divided by total number of subjects assigned to each treatment group from the full analysis set.

For a subject who discontinued study treatment early (see Section 5.2.2.1), the subject will be followed to Day 150 for assessment of primary endpoint events. The event observed after the early termination of study treatment will be counted as an event and will be included in the primary analysis.

For early termination subjects (ie, those who did not complete Day 150 visit), the primary endpoint will be handled according to the following rules in the primary analysis:

- Early termination subjects who had a primary endpoint event during the 150-day efficacy assessment period (regardless of treatment status, ie, whether the subject received all study drug doses or discontinued dosing) will be used in the primary analysis and included as "event occurred". [No imputation]
- Direct imputation of missing primary endpoint at Day 150 visit:
  - Subject deaths prior to Day 150 that are adjudicated to be RSV related will be included as "event occurred".
  - Remaining early termination subjects (including non-RSV deaths) across all treatment groups, will be imputed to the average placebo score (estimated placebo event rate). The approach to estimating the placebo event rate is the Kaplan-Meier estimate at Day 150.
- Imputed scores along with observed subject data will be utilized in the Cochran-Mantel-Haenszel analysis. Imputed scores along with observed subject data will be utilized in the Cochran-Mantel-Haenszel (CMH) analysis (with stratum adjusted by Mantel-Haenszel method).

As a sensitivity analysis to the primary endpoint, the following analyses will be performed:

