2.2. Sample Size and Power Considerations

Originally Planned Sample Size

For Part B, the sample size estimation is based on the primary efficacy endpoint of medically attended RSV infection (hospitalization or outpatient LRTI). Literature ([Hall 2009](#), [Ambrose 2014](#)) show that the event rate in this endpoint is in the range of 12% to 22% in the studied infant populations. The Hall data is population based and the majority of infants are full-term; the Ambrose publication of data from the RSV Respiratory Events Among Preterm Infants Outcomes and Risk Tracking (REPORT) study evaluated preterm infants of 32-35 weeks gestational age and less than 6 months of chronological, whom were not receiving RSV prophylaxis. As the event rate may vary over RSV season or geographic region, a relatively conservative approach was taken to assume that event rate is 10% for the placebo group, and either dosing regimen of REGN2222 would reduce the event rate from placebo by 60% (event rate of 4%). With 505 randomized subjects per arm or a total of 1515 randomized subjects, the study would have 90% power to demonstrate a 60% or greater reduction at 2-sided significance level $\alpha=0.025$. This originally planned sample size also incorporated a 5% early dropout rate. The sample size calculation was based on chi-square test with continuity correction and performed using nQuery version 7.0 (Statistical Solutions Ltd, Cork, Ireland).

Based on the originally planned sample size and event rate assumption, we anticipated approximately 90 primary endpoint events.

The blinded sample size re-estimation (as detailed in the study protocol Section 9.2.1) designed for the originally planned sample size has not been performed for this study.

Power Calculation for Reduced Sample Size

[figure not shown]
The sample size of the study has been reduced due to business considerations. The intent of this power calculation is to understand the impact of the reduced sample size on the primary efficacy analysis. Specifically, to accommodate the reduced sample size, the overall Type I error for the pairwise comparisons of each REGN2222 dose regimen to placebo will be controlled using a

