pre-specified hierarchical inferential approach (2-sided $\alpha=0.05$ for each statistical test; see Section 5.7.3), as opposed to the originally planned Bonferroni adjustment (2-sided $\alpha=0.025$ for each pairwise treatment comparison). Therefore, assuming approximately 1200 subjects are administered study drug, the comparison of the REGN2222 2-dose regimen to placebo will have approximately 87% power to detect the previously planned 60% reduction in medically attended RSV infections with a 2-sided significance level of 0.05.

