Missing Data Handling for the Primary Efficacy Endpoint

For early termination (ET) subjects those who did not complete the 150-day efficacy assessment period, their primary endpoint will be handled according to the following rules in the primary analysis:

- Early termination subjects who had a primary endpoint event during the 150-day efficacy assessment period (regardless of treatment status, ie, whether the subject received all study drug doses or discontinued dosing) will be used in the primary analysis and included as “event occurred”. [Observed, thus no imputation]
- Direct imputation of missing primary endpoint at Day 150 visit:
 - Subject deaths prior to Day 150 that are adjudicated to be RSV related will be included as “event occurred” at the onset date of the adverse event that led to death.
 - Remaining early termination subjects (including non-RSV deaths) across all treatment groups, will be imputed to the average placebo score (estimated placebo event rate).
 - Approach to estimating the placebo event rate is the Kaplan-Meier (KM) estimate at Day 150 based on all randomized subjects in the placebo group. Early termination subjects in the placebo group who had no primary endpoint event will be censored in the KM procedure at the last time point when their primary endpoint event is assessed (ie, at the last visit completed by the subject, scheduled or unscheduled, prior to Day 150 visit). Placebo subjects who completed Day 150 visit with no primary endpoint event will be censored at the date of their Day 150 visit. The derivation of study day is detailed in Appendix 11.3.
- Imputed scores along with observed subject data will be utilized in the Cochran-Mantel-Haenszel (CMH) analysis.

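### Infants who leave early are imputed the full 150-day placebo rate even for time already observed event-free; compared with imputing only the remaining risk, this inflates the arm with more dropouts

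*SAP*

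**What the plan says.** Early-termination infants with an observed event, or with a death adjudicated as RSV related, count as events. For the others, Protocol 9.5.2.1 states: "Remaining early termination subjects (including non-RSV deaths) across all treatment groups, will be imputed to the average placebo score". SAP 4.6.1 repeats that such infants "will be imputed to the average placebo score (estimated placebo event rate" and defines the rate as the Day-150 KM estimate in the placebo arm, with placebo dropouts censored at their last completed visit.

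SAP 5.7.1 puts this into the estimator. In each arm and stratum, the number of missing infants times that single rate is added to the observed events. Nothing conditions the rate on follow-up already completed. The same rule serves the secondary endpoint (SAP 4.6.2), the components (5.7.1.4), the subgroups (5.7.1.7) and several exploratory proportions (5.7.4).

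Three other analyses bear on missing data:
- The observed-case analysis (SAP 5.7.1.3) counts event-free dropouts as non-events.
- The tipping-point analysis (SAP 5.7.1.3) multiplies the imputed rate in the REGN2222 arms only.
- The log-rank and Cox analyses (SAP 5.7.4) censor dropouts.

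**The concern.** The plan treats the same information in two ways. When it estimates the placebo rate, an infant followed event-free to Day 140 contributes 140 days of survival. When it imputes that infant, those days vanish and the score is the whole 150-day risk.

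With a 10% placebo rate and constant hazard, the risk remaining at Day 140 is 1 - 0.90^(10/150) = 0.7%. At Day 113 it is 1 - 0.90^(37/150) = 2.6%. Both infants are scored 10%.

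Each dropout therefore adds a surplus to its own arm. If dropout is balanced, the surpluses nearly cancel in the risk difference. If it is not, the primary estimate carries an artefact that reflects retention rather than efficacy. When the placebo arm loses more infants, the artefact points toward REGN2222.

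**Working it through.** **Inputs from the documents.** Protocol 9.2: "it is assumed that event rate is 10% for the placebo group". REGN2222 rate 4%, 505 per arm, 5% dropout, and a chi-square test with continuity correction (Protocol 9.2, SAP 2.2). For the reduced trial, "assuming approximately 1200 subjects are administered study drug", or 400 per arm at 1:1:1.

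**The plan's own figures.** 10% vs 4%, two-sided 0.025, 90% power, continuity correction: 480 per arm. 480/0.95 = 505.3, against 505 stated. With 400 x 0.95 = 380 per arm at two-sided 0.05, power is 87.4%. SAP 2.2 states "approximately 87% power to detect the previously planned 60% reduction in medically attended RSV infections with a 2-sided significance level of 0.05". Both reproduce.

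**Assumptions not in the documents.** Constant hazards; dropout independent of events and uniform over 150 days; a fraction cP of placebo and cA of REGN2222 infants with a dropout time; one stratum.

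**Current rule.** Mean event-free probability at the dropout time is M = (1 - S(150)) / (-ln S(150)). Mean score of a dropout is (1 - M) + 0.10 M.
- Placebo: M = 0.10/0.10536 = 0.9491; score 0.0509 + 0.0949 = 14.58%, which is 4.58 points above 10%.
- REGN2222: M = 0.04/0.04082 = 0.9799; score 0.0201 + 0.0980 = 11.81%, which is 7.81 points above 4%.

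Risk difference in points: -6.00 + 7.81 cA - 4.58 cP. At 5% dropout the placebo arm is analysed at 10 + 0.05 x 4.58 = 10.23%, against its own KM of 10.00%.

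**Remaining-risk rule, 1 - S(150)/S(t) from the placebo curve.** The placebo surplus is zero. For REGN2222, the mean of S_A/S_P is (0.96/0.90 - 1)/ln(0.96/0.90) = 0.06667/0.06454 = 1.0330. The score is 1 - 0.90 x 1.0330 = 7.03%, which is 3.03 points above 4%. Risk difference: -6.00 + 3.03 cA.

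**Artefact (current minus remaining-risk).** 4.78 cA - 4.58 cP points:

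| Dropout placebo/REGN2222 | Current | Remaining-risk | Artefact |
|---|---|---|---|
| 5%/5% | -5.84 | -5.85 | +0.01 |
| 7%/5% | -5.93 | -5.85 | -0.08 |
| 8%/2% | -6.21 | -5.94 | -0.27 |
| 2%/8% | -5.47 | -5.76 | +0.29 |
| 10%/0% | -6.46 | -6.00 | -0.46 |

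**Equal true rates of 10%.** The artefact is the whole bias: 4.58 (cA - cP). At 8%/2% it is -0.27; at 10%/3% it is -0.32.

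**Total bias at the design effect.** It favours REGN2222 only if 4.58 cP > 7.81 cA, so cP/cA > 1.71. The ratio is about 1.1 if all dropout falls at 90% of follow-up and about 3.0 at 25%.

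**Error rate.** 20,000 simulated trials, 400 per arm, SAP 5.7.1 variance, equal rates of 10%. The share of trials significant in favour of REGN2222 (nominal 2.5%) is 2.3% with no dropout, 2.2% at 5%/5%, 3.1% at 8%/2%, about 3.2% at 10%/3% and 4.6% at 10%/0%. Under the remaining-risk rule it is 2.4% at 10%/3% and between 2.0% and 2.7% in all scenarios run. The standard error of the difference is about 2.1 points at 10%/3%.

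**The case against.** The strongest reply concerns direction. A reader might infer that the rule biases the result toward whichever arm has fewer dropouts, so that any excess of placebo dropout flatters REGN2222. That is not supported. It is exact for total bias only when the true rates are equal. At 10% vs 4%, giving REGN2222 dropouts the placebo rate costs more per infant (7.81 points) than the surplus in placebo (4.58), so 7%/5% dropout still gives -5.93, toward no effect. What favours the arm with fewer dropouts in general is the artefact alone. This part of the reply stands and limits the point.

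Second, the documents give no per-arm dropout or timing, and Part B is double-blind with injections in every arm, so nothing in them predicts a threefold imbalance. This stands: the imbalanced scenarios are illustrations. At the planned 5% in both arms the artefact is negligible, and even -0.32 points is small beside a standard error of about 2.1.

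Third, safeguards exist. Disposition by arm (SAP 5.5) will expose an imbalance. The observed-case analysis moves the opposite way when placebo loses more infants. The log-rank and Cox analyses use event-free time as observed. This stands in part: their p-values are descriptive, observed-case goes to the other extreme, and the time-to-event analyses do not estimate the risk difference. The tipping-point analysis leaves placebo at the full rate and so does not test this direction.

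Finally, neither document calls the rule conservative, so showing that it is not always so rebuts no claim made there.

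**Conclusion.** The point holds as a flaw in the imputation rule, not as a demonstrated bias in this trial. The rule discards event-free time that the plan's own KM step uses. Relative to imputing the remaining placebo risk, this raises the arm with more dropouts: about zero at equal dropout, -0.27 points at 8%/2% placebo/REGN2222, and -0.32 points at 10%/3% under equal rates, where one-sided error is about 3.2% instead of 2.5%. At the design effect, total bias turns in favour of REGN2222 only beyond a dropout ratio of about 1.7 with uniform timing; below that it runs toward no effect.

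The sizes rest on assumed per-arm dropout, uniform timing, constant hazard and independent dropout. Part of the simulated excess error may come from a variance that treats imputed scores as observed, which is a separate matter. The change is worth making because balanced dropout cannot be guaranteed in advance and the correction costs nothing in the estimate when dropout is balanced.

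**What to change.** In SAP 4.6.1 and Protocol 9.5.2.1, impute each remaining early-termination infant, in every arm, with 1 - S(150)/S(t), where S is the placebo KM curve already being estimated and t is the infant's last assessment day. Keep the current rule as a sensitivity analysis. This still allows for RSV after leaving the study, which is the purpose given in the amendment rationale, and still credits no drug benefit after dropout. In the scenarios run, the remaining bias is zero or toward no effect.

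Costs:
- The formulas in SAP 5.7.1 to 5.7.1.3 that use one rate times the number missing (estimator, variance, Fisher and logistic counts, tipping-point multiplier) must use the sum of individual scores, and analyses that inherit the rule must follow.
- The protocol text needs an amendment. Protocol 9 and SAP 1 allow SAP revision before database lock.
- If t is the last scheduled visit rather than the true dropout day, some bias remains: about 0.07 of the 0.32 points at 10%/3%, since scheduled visits are 28 to 37 days apart. Early-termination and unscheduled visits reduce it.
- Informative dropout would affect both rules.

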4.6.2. Secondary Efficacy Variable

The secondary efficacy variable is the proportion of FAS subjects who have RSV-confirmed hospitalization, ER, UC, or pediatric clinic visits (for upper or lower respiratory infection) during the 150-day efficacy assessment period. This secondary endpoint will be derived in the same way as the primary endpoint (including imputation for missing endpoint event) except that the RSV-confirmed outpatient visit (ER, UC, or pediatric clinic visits) can be for either upper or lower respiratory infection (ie, Question 4 in [Figure 2](#) can have the answer of either YES or NO). For ET subjects who did not complete Day 150 visit, their secondary endpoint will be handled according to the same rule as specified for the primary endpoint, with secondary endpoint event in place of primary endpoint event in the rule.

4.6.3. Exploratory Efficacy Variable(s)

Other secondary efficacy variables will be studied as exploratory endpoints and include the following measures during the 150-day efficacy assessment period:

- 1) Number of days from first dose of study drug to first **primary** efficacy endpoint event. Subject deaths prior to Day 150 that are adjudicated to be RSV related will be included as event at the onset date of the adverse event that led to death. For subjects who didn't have a primary efficacy endpoint event, this endpoint will be defined as the number of days from the first dose of study drug to the last time point when their primary endpoint is assessed, ie, Day 150 visit or last visit completed for ET subjects.
- 2) Number of days from first dose of study drug to first **secondary** efficacy endpoint event. Subject deaths prior to Day 150 that are adjudicated to be RSV related will be included as event at the onset date of the event that led to death. For subjects who didn't have a secondary efficacy endpoint event, this endpoint will be defined as the number of days from the first dose of study drug to the last time point when their secondary endpoint is assessed, ie, Day 150 visit or last visit completed for ET subjects.
- 3) Proportion of FAS subjects with RSV-confirmed hospitalization.
- 4) Total number of RSV-associated hospital visits (for upper or lower respiratory infection).
- 5) Total number of RSV-associated ER visits (for upper or lower respiratory infection).
- 6) Total number of RSV-associated UC visits (for upper or lower respiratory infection).
- 7) Total number of RSV-associated pediatric clinic visits (for upper or lower respiratory infection) visits.
- 8) Concomitant medications or procedures associated with RSV infection.
- 9) Total number of all-cause respiratory illness-associated hospital visits (for upper or lower respiratory infection).
- 10) Total number of all-cause respiratory illness-associated ER visits (for upper or lower respiratory infection).
- 11) Total number of all-cause respiratory illness-associated UC visits (for upper or lower respiratory infection).
- 12) Total number of all-cause respiratory illness-associated pediatric clinic visits (for upper or lower respiratory infection).
- 13) Concomitant medications or procedures for all-cause respiratory illness.
- 14) Repeat items 9) through 13) above with the single exception to count the number of all-cause respiratory illness-associated visits **after** the initial episode of RSV illness.
- 15) Total number of days with RSV-associated mechanical ventilation for subjects with RSV-confirmed hospitalizations.
- 16) Total number of days with RSV-associated supplemental oxygen for subjects with RSV-confirmed hospitalizations.

- 17) Total length of stay in hospital for subjects with RSV-confirmed hospitalizations.
- 18) Total number of missed days of work for parent(s) or guardian(s) associated with each medically attended RSV event.
- 19) Number and prevalence rate of other common respiratory pathogens identified by a RT-PCR multiplex respiratory panel for nose swab specimens determined to be negative for RSV (using the protocol specified Lyra RT-PCR assay [Quidel Molecular RSV/hMPV assay]).
- 20) Proportion of FAS subjects with the primary endpoint event, with the single exception of using an alternative definition for LRTI.

Instead of the LRTI definition in Section 4.6.1, the following definition of LRTI will be used for medically attended RSV infection (hospitalization or outpatient LRTI) as agreed in the Pediatric Investigational Plan (PIP) :

Infant with RSV-proven infection who presents with cough or difficulty breathing **and 2** of the following criteria:

- Lower chest wall indrawing
- Hypoxemia (peripheral capillary oxygen saturation <95% breathing room air)
- Wheezing or crackles
- Ventilatory failure (needing ventilator support in any form)
- New onset apnea
- Increased respiratory rate using WHO criteria for fast breathing for age ([Wingerter 2012](#)) as below:

| Age | Increased Respiratory Rate (breaths/min) |
|--------------------|------------------------------------------|
| < 60 days | ≥ 60 |
| 60 - 364 days | ≥ 50 |
| 365 days - 5 years | ≥ 40 |

Age in days = Onset date of the episode of RSV illness – birth date +1.

- 21) Proportion of FAS subjects with the primary endpoint event, with the single exception of the removal of RSV hospitalization non-LRTI.
- 22) Proportion of FAS subjects with the primary endpoint, with the single exception of accepting positive RSV detection results from the multiplex RT-PCR respiratory panel in deriving the primary endpoint event.
- 23) Proportion of FAS subjects with the secondary efficacy endpoint, with the single exception of accepting positive RSV detection results from the multiplex RT-PCR respiratory panel in deriving the secondary efficacy endpoint event.

Note 1: For a RSV RT-PCR test to be considered positive for the analysis, the specimen collection has to occur within a 14 day period since the onset of the episode of RSV illness.

Note 2: All-cause respiratory illness is defined as without consideration of RSV positivity or negativity.

4.7. Safety Variables

Subject safety will be assessed through the collection of AEs, laboratory data (hematology, chemistry), vital signs, and physical exam (including weight). For these measures, with the exception of the AEs, all measurements will be assigned to analysis windows for temporal summaries. Unless otherwise noted (eg, AEs), baseline for these measures is defined as the last chronologically available valid assessment prior to the first dose of study drug.

The period of safety observation starts from the time when the informed consent is given and continues into the following periods:

- The PRE-TREATMENT period: defined as the day from the signed informed consent form (ICF) to before the first study drug injection.
- The SAFETY TREATMENT period: defined as the day from the first study drug injection up to the day of the last study drug injection plus 180 days.
- The POST-TREATMENT period: defined as starting the day after the end of the SAFETY TREATMENT period.

